	All continuous efficacy data will be summarized descriptively by treatment group and time point including changes from baseline (n, arithmetic mean, standard deviation, minimum, Q25, median, Q75 and maxi-
	mum),

[figure not shown]

Table 1: Schedule of visits and assessments

	TV	FUV1	FUV2	cFUV ¹	FUV3	SC	FUV4 ²
Study visit assessment	(D0)	(D3±1)	(D7±2)	(D14±3)	(D28±5)	(D56±7)	(D91±7)
Informed consent	0						***
Inclusion and exclusion criteria	•						
Demography/baseline characteristic							
Medical history (incl. hearing loss onset)	•						
Prior and concomitant medication recording		6	•	•	•	6	0
Tinnitus evaluation (history, characteristics)		•3	• ³		•3		• ³
Physical examination							
Vital signs (blood pressure, temperature, pulse)		•	•		•		0
Laboratory test (hematology, biochemistry)		•					
Laboratory test (virology)							
Urine pregnancy test, if applicable							•
HHIA questionnaire					•		0
PGIC _{hearing loss} Scale			•		•		0
Tinnitus presence or absence and numerical rating scales (TLQ _{Loudest} , TAQ _{Worst})			Subject diary				
Otoscopy/microscopy	•	•	0	•	•		•
Tympanometry			• ⁴	•4	0		•
Pure tone audiometry (air and bone conducted)		•	0		•		•
Speech audiometry (WRS at 80 dB in quiet)	• ^{5,6}		6		•		0
Speech audiometry (WRS at 60 dB in quiet)	• ^{5,6}						8
Spontaneous nystagmus (Frenzel goggles or VNG)	• ⁵	0	•		•		•
Balance test (Romberg's test)	•5	8	0		•		6
Suicidality questionnaire (C-SSRS)			6		6		
Final eligibility check prior to randomization	0						· · · · · · · · · · · · · · · · · · ·
Randomization							
IMP intratympanic injection	6						
Background therapy (corticosteroid) ⁷	•						
Dispense background therapy documentation card ⁷	•						
Check completion of background therapy documentation card ⁷		•	•	•	•		
Adverse event reporting	•	•	•	•	•	•	•

Only to be performed if eardrum is not closed at FUV2 at D7.

² Or premature end of trial visit in case the subject terminates the trial prematurely.

³ Only to be performed if tinnitus is present.

⁴ Only to be performed if eardrum is fully closed.

⁵ Assessment to be repeated, at the earliest, 24 hours from onset if subject presenting within the first 24 hours from ISSNHL onset. If eligibility is confirmed, this second assessment serves as baseline measure.

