2.4 Trial rationale

Clinical experience with AM-111 shows that a single dose of intratympanic AM-111 at a concentration of up to 2.0 mg/mL is well tolerated, and that the drug product is safe. Trial outcomes showed rapid and clinically relevant improvement in various measures of hearing function, speech discrimination and also in ASNHL-related tinnitus.

The present trial aims to demonstrate and confirm that a single dose of AM-111 0.4 mg/mL will provide a therapeutic benefit through a significant improvement in hearing following an incident of severe to profound ISSNHL. An improvement in hearing threshold of ≥10 dB is considered as clinically relevant. Improvement in hearing recovery shall be supported by improvement in word recognition in quiet as well as in the rate of complete tinnitus remission. The trial shall further evaluate potential incremental treatment benefits from the use of a higher concentration, 0.8 mg/mL, and the safety and local tolerance of AM-111.

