6.6.4.3 Tinnitus numerical rating scales

The presence or absence of tinnitus and numerical rating scales for subjective tinnitus loudness "at its loudest" ($TLQ_{Loudest}$) and subjective tinnitus annoyance "at its worst" (TAQ_{Worst}) is self-administered at all visits from FUV1 until FUV4, for the $TLQ_{Loudest}$ and TAQ_{Worst} also at TV.

At TV, the presence or absence of tinnitus is assessed by the investigator, using the questionnaire in Appendix 1.

In addition, a subject diary will be used for the subjects to self-record weekly the presence or absence of tinnitus and numerical rating scales. If a subject diary entry is missing within \pm 4 days of a visit, it may be replaced by the visit based values. Subjects will not have access to their previous ratings. Complete remission of ISSNHL-related tinnitus will be given as soon as a subject rates both $TLQ_{Loudest}$ and TAQ_{Worst} as 0, and answers the question about tinnitus presence with "No". Refer to Appendices 1 and 2.

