10.1.2 Secondary efficacy endpoints

[figure not shown]
The following secondary efficacy endpoints will be evaluated in this study:

[figure not shown]
Main secondary efficacy endpoint:

• Absolute improvement in WRS_(80dB) from baseline to FUV4. An improvement in WRS of at least 15 percentage points is considered clinically relevant.

Other secondary efficacy endpoints:

- Absolute improvement in PTA from baseline to FUV1, FUV2 and FUV3;
- Absolute improvement in WRS_(80 dB) from baseline to follow-up visits FUV1, FUV2 and FUV3; and
- Frequency of complete tinnitus remission in subjects with ISSNHL-related tinnitus at baseline, determined at FUV4. Complete tinnitus remission is achieved when a subject rates both TLQ_{Loudest} and TAQ_{Worst} as zero, and answers the question about tinnitus presence with "No".

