10.2.2 Secondary safety endpoints

- Occurrence of clinically relevant hearing deterioration in the treated ear (air conduction) from baseline to all FUVs (other than FUV3);
- Difference in occurrence of clinically relevant hearing deterioration from baseline to all FUVs between treated and untreated contralateral ear;
- Occurrence and severity of Adverse Events (AEs) and Serious Adverse Events (SAEs), assessed for causal relationship with respect to:
 - o The IMP;
 - o The intratympanic IMP administration procedure.

11 Statistical methods and data analysis

A statistical analysis plan (SAP) will detail the statistical evaluation. This plan is finalized prior to unblinding. In particular, changes of planned analyses outlined in the trial protocol will be documented in the SAP. Deviations from the approved SAP will be documented in the clinical trial report.

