9.2.2 The Other Secondary Efficacy Endpoints Analysis

All other secondary efficacy endpoints will be summarized in the Efficacy Analysis Set as described below.

[figure not shown]
- Absolute improvement in PTA from baseline to FUV1, FUV2 and FUV3;
- Absolute improvement in WRS_(80 dB) from baseline to follow-up visits FUV1, FUV2 and FUV3;

The absolute improvements are continuous data which will be summarized descriptively.

• Frequency of complete tinnitus remission in subjects with ISSNHL-related tinnitus at baseline, determined at FUV4. Complete tinnitus remission is achieved when a

Page 30 of 65

subject answers the question about tinnitus presence with "No". Frequency of complete tinnitus remission will be summarized categorically.

Statistical Analysis Plan	Auris Medical Protocol #AM-111-CL-15-0
Version 1.0	

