11 INTERIM ANALYSES

[figure not shown]
Due to the study being terminated early, the interim analysis is not performed.

Page 40 of 65

Due to the early termination of the study, only 56 subjects are enrolled. The following are changes from the protocol:

- Only partial and missing dates of adverse events and medications are imputed to determine treatment emergence or determine the prior and concomitant medications. All other Imputation of missing values specified in the Protocol section 11.2 is not performed.
- Due to the small sample size, only descriptive analysis is performed in efficacy and safety endpoints.
- Interim analysis will not be performed and conditional power will not be calculated.
- Additional enrollment of subjects based on the results of interim analysis is no longer applicable.
- Tinnitus complete remission is considered given when the subject answers the question about tinnitus presence with "No"; it is not required that in addition both the Tinnitus Loudness Question (TLQ_{Loudest}) and Tinnitus Annoyance Question (TAQ_{Worst}) are rated as zero.
- Addition of analysis of efficacy outcomes by severity subgroup (profound / ≥ 90 dB PTA, severe / < 90 dB PTA at baseline).

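### The SAP counts complete tinnitus remission on a presence answer of 'No' alone, and its table titles show no summary of the protocol's three-condition rate

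*SAP*

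**What the plan says.** Protocol 6.6.4.3 sets the rule: "Complete remission of ISSNHL-related tinnitus will be given as soon as a subject rates both" TLQ(Loudest) and TAQ(Worst) as 0 and also answers 'No' on presence. Protocol 10.1.2 repeats it for the endpoint: "Complete tinnitus remission is achieved when a subject rates both" scales as zero, again together with 'No'.

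SAP 9.2.2 keeps the endpoint, "Frequency of complete tinnitus remission in subjects with ISSNHL-related tinnitus at baseline, determined at FUV4", but counts it as met when a "subject answers the question about tinnitus presence with" 'No'. SAP section 12 lists this among the changes from the protocol: "it is not required that in addition both the Tinnitus Loudness Question" and the Tinnitus Annoyance Question be zero. The lead-in to that list is early termination with 56 subjects enrolled. No reason specific to this change is given.

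SAP 7.4 says that presence and both ratings are collected at all visits from TV to FUV4. SAP section 16 plans one remission table (14.2.3.2.1), one table of loudness and annoyance (14.2.3.2.2) and a by-visit listing of presence and ratings (16.2.6.3).

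**The concern.** Complete remission of ISSNHL-related tinnitus is a named secondary objective. Protocol 2.4 wants the hearing result supported by improvement in word recognition "as well as in the rate of complete tinnitus remission". A reader of the report will see a rate under the protocol's endpoint name and will tend to take it as the protocol's endpoint.

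The SAP's rule is looser. A subject who answers 'No' at FUV4 but has a recorded non-zero loudness or annoyance rating counts as a complete remission under the SAP and not under the protocol. Early termination explains why the interim analysis, the imputation and the inferential tests were dropped. It does not explain why one subject's remission status should be decided differently. If only the looser rate is tabulated, the report gives no by-arm answer to whether the prespecified rate is lower.

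**Working it through.** The documents state no figure for this endpoint, so there is none to reproduce. The check compares definitions and then works out the weight of one subject.

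**Definitions side by side**

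| Condition | Protocol 6.6.4.3 and 10.1.2 | SAP 9.2.2 and 12 |
|---|---|---|
| TLQ(Loudest) = 0 | required | dropped |
| TAQ(Worst) = 0 | required | dropped |
| Presence answered 'No' | required | required |

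**Direction.** Subjects who meet all three conditions are a subset of those who answer 'No'. With the same presence item and the same denominator n,

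SAP rate − protocol rate = d / n ≥ 0,

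where d is the number who answer 'No' without meeting both rating conditions. The sign is fixed only if both rates use the same subjects. If subjects with blank ratings were removed from one denominator alone, the ordering could fail.

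**Can d be above zero?** Follow-up uses two presence questions, one about right now and one about the past week (Protocol Appendix 1, SAP Appendix 2). The visible SAP text does not say which one decides. The ratings ask for loudness at its loudest and annoyance at its worst. If the 'right now' question decides, a subject with intermittent tinnitus could answer 'No' and still give a non-zero rating. The rating form is redacted, so this is a possibility and not a finding.

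**Weight of one subject**

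- Enrolled: 56 (SAP sections 4 and 12). Allocation: 1:1:1.
- Average arm: 56 / 3 = 18.67. Protocol 5.3.1 treats enrolled as consent signed, so the number randomized may be lower. This is an average; an individual arm can be larger.
- The share of an arm that enters the denominator (in the Efficacy Analysis Set, with ISSNHL-related tinnitus at baseline) is not given. It is an assumption, shown as a range.

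| Assumed share of the average arm | n | 100 / n |
|---|---|---|
| 100% | 18.67 | 5.4 points |
| 80% | 14.93 | 6.7 points |
| 60% | 11.20 | 8.9 points |
| 40% (80% in the set × 50% with tinnitus) | 7.47 | 13.4 points |

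Missing FUV4 data would shrink n further. These figures are 1/n and would apply to any binary endpoint here; they say nothing about how many subjects are reclassified.

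**The case against.** The strongest reply is that the protocol's own procedure was followed. Protocol section 11 asks that "changes of planned analyses outlined in the trial protocol will be documented in the SAP", and SAP section 12 does so, naming both dropped ratings. It requires no rationale for each change. This stands: there is no breach and no undisclosed change.

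A reader might infer that the definition was loosened after seeing results, because the SAP text postdates the recruitment stop of 28Nov2017. The documents do not support that. Protocol section 11 has the SAP finalized before unblinding, SAP 4.3 keeps the blind, and no interim analysis was done.

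A reader might also infer that the protocol's rate is hidden or certainly unplanned. Neither follows. Listing 16.2.6.3 gives presence and ratings per subject, so the three-condition status can be worked out by hand. Section 16 gives titles only, so a row inside Table 14.2.3.2.1 cannot be ruled out. But a listing is not a by-arm summary of a prespecified endpoint, and none is visible.

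Finally, the form may skip the ratings after 'No', in which case the two definitions would coincide for those subjects. That is less likely but not excluded. The protocol's rule presupposes ratings recorded beside a 'No'. Table 1 limits the tinnitus history and characteristics row to subjects with tinnitus at follow-up but shows no such limit on the row "Tinnitus presence or absence and numerical rating scales". The form itself is redacted and that row's visit marks are lost. This objection does change the remedy: if a skip exists, simply excluding blank ratings would push the protocol-defined rate towards zero.

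**Conclusion.** The point holds, and it is modest. The SAP openly replaces a three-condition endpoint with one condition under the same name. The only reason shown does not bear on classification, and no by-arm summary of the prespecified rate is visible although the data for it are collected. The direction is certain for the same presence item and the same evaluable subjects: the SAP rate is equal or higher. The size is unknown and may be zero. One subject is worth about 5.4 points in an average arm if every subject enters the denominator, and more under any smaller assumed share.

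It would go too far to say that the reported rate will be inflated, since the documents give no discordance rate. The endpoint is a descriptive 'other secondary' one, so no test, error rate or power is touched.

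**What to change.** First check the tinnitus form. Then, in Table 14.2.3.2.1, report FUV4 remission by arm in two rows:

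- the protocol's definition: TLQ(Loudest) = 0, TAQ(Worst) = 0 and presence 'No';
- the 'No'-only rate, labelled as the modified definition.

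Use one named presence item ('right now' or 'past week') for both rows. Use one denominator: Efficacy Analysis Set subjects with ISSNHL-related tinnitus at baseline. SAP 5.1.2.2 and 9.2.2 already restrict the endpoint to those with such tinnitus, so this only labels the table.

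Handle blank ratings according to the form:

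- If ratings are skipped by design after 'No', treat those subjects as meeting the rating conditions and footnote that the two definitions coincide for them.
- If ratings were required but are blank, show those subjects in a separate Missing row, as SAP 14.2.5.2 already provides. Give the protocol-defined rate both with and without them, that is, once counting them as remissions and once not, over the same denominator.

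The cost is one derivation on data already collected, one or two extra rows, and possibly a lower remission percentage.

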14 SPECIFICATIONS

All tables, listings, figures (TLFs), and statistical analyses will be generated using Computer-generated table, listing and figure output will adhere to the following specifications.

14.1. GENERAL CONSIDERATIONS

- One output file can contain several outputs. / Each output will be stored in a
- Output files will be delivered in rtf format.
- Numbering of TLFs will follow International Conference on Harmonisation (ICH) E3 guidance.

14.2. TABLE, LISTING, AND FIGURE FORMAT

14.2.1. General

separate file.

- All TLFs will be produced in landscape format, unless otherwise specified.
- All TLFs will be produced using the Courier New font, size 8.
- The data displays for all TLFs will have a minimum 1-inch margin on all 4 sides.
- Headers and footers for figures will be in Courier New font, size 8.
- Legends will be used for all figures with more than 1 variable, group, or item displayed.
- TLFs will be in black and white (no color), unless otherwise specified
- Specialized text styles, such as bolding, italics, borders, shading, and superscripted and subscripted text, will not be used in the TLFs, unless otherwise specified. On some occasions, superscripts may be used (see below).
- Only standard keyboard characters will be used in the TLFs. Special characters, such as non-printable control characters, printer-specific, or font-specific characters, will not be used. Hexadecimal-derived characters will be used, where possible, if they are appropriate to help display math symbols (e.g., μ). Certain subscripts and superscripts (e.g., cm2, Cmax) will be employed on a case-by-case basis.
- Mixed case will be used for all titles, footnotes, column headers, and programmersupplied formats, as appropriate.

14.2.2. Headers

All output should have the following header at the top left of each page:
 Auris Medical
 Protocol AM-111-CL-15-01

- All output should have Page n of N at the top or bottom right corner of each page. TLFs should be internally paginated in relation to the total length (i.e., the page number should appear sequentially as page n of N, where N is the total number of pages in the table).
- The date output was generated should appear along with the program name as a footer on each page.
- TLFs should be internally paginated in relation to the total length (i.e., the page number should appear sequentially as page n of N, where N is the total number of pages in the table).
- Except TLF specific footnotes, all outputs should include the following at the bottom of each page:

Program:

Table/Listing/Figure Generation: DDMMYYYY HH:MM

14.2.3. Display Titles

• Each TLF will be identified by the designation and a numeral. (i.e., Table 14.1.1). ICH E3 numbering is used . A decimal system (x.y and x.y.z) will be used to identify TLFs with related contents. The title is centered. The analysis set should be identified on the line immediately following the title. The title and table designation are single spaced. A solid line spanning the margins will separate the display titles from the column headers. There will be 1 blank line between the last title and the solid line.

Table x.y.z
First Line of Title
Second Line of Title if Needed
(Efficacy Analysis Set)

14.2.4. Column Headers

• Analysis set sizes will be presented for each treatment arm in the column heading as (N=xx) (or in the row headings if applicable). This is distinct from the 'n' used for the descriptive statistics representing the number of subjects in the analysis set.

14.2.5. Body of the Data Display

14.2.5.1. General Conventions

Data in columns of a table or listing should be formatted as follows:

- alphanumeric values are left-justified;
- · whole numbers (e.g., counts) are left-justified; and
- numbers containing fractional portions are central aligned.

14.2.5.2. Table Conventions

• Units will be included where available

INC Research #1006680

Version 1.0

• If the categories of a parameter are ordered, then all categories between the maximum and minimum category should be presented in the table, even if n=0 for all treatment arms in a given category that is between the minimum and maximum level for that parameter. For example, the frequency distribution for symptom severity would appear as:

Severity	N
Rating	
severe	0
moderate	8
mild	3

[figure not shown]
Where percentages are presented in these tables, zero percentages will not be presented and so any counts of 0 will be presented as 0 and not as 0 (0%).

- If the categories are not ordered (e.g., Medical History, Reasons for Discontinuation from the Study, etc.), then only those categories for which there is at least 1 subject represented in 1 or more groups should be included.
- An Unknown or Missing category should be added to any parameter for which information is not available for 1 or more subjects.
- Unless otherwise specified, the estimated mean, Q25, median and Q75 for a set of values should be printed out to 1 more significant digit than the original values, and standard deviations should be printed out to 2 more significant digits than the original values. The minimum and maximum should report the same significant digits as the original values. For example, for systolic blood pressure:

N	XX
Mean	XXX.X
Median	XXX.X
Std Dev	X.XX
Q1, Q3	XXX, XXX
Min, Max	XXX, XXX

- P-values should be output in the format: "0.xxx", where xxx is the value rounded to 3 decimal places. Any p-value less than 0.001 will be presented as <0.001. If the p-value should be less than 0.0001 then present as <0.0001. If the p-value is returned as >0.999 then present as >0.999
- Percentage values should be printed to one decimal place, in parentheses with no spaces, one space after the count (e.g., 7 (12.8%), 13 (5.4%)). For values that round down to 0.0, it will be displayed as '<0.1'. Unless otherwise noted, for all percentages, the number of subjects in the analysis set for the treatment arm who have an observation will be the denominator. Percentages after zero counts should not be displayed and percentages equating to 100% should be presented as 100%, without any decimal places.

- Tabular display of data for medical history, prior / concomitant medications, and all tabular displays of adverse event data should be presented by the ATC level 2, ATC level 4 or SOC with the highest occurrence in the "Overall" column in decreasing order, assuming all terms are coded. Within the ATC level 2, ATC level 4, or SOC, medical history (by preferred term), drugs (by preferred term), and adverse events (by preferred term) should be displayed in decreasing order. If incidence for more than 1 term is identical, they should then be sorted alphabetically.
- For categorical summaries (number and percentage of subjects) where a subject can be included in more than one category, describe in a footnote or programming note if the subject should be included in the summary statistics for all relevant categories or just 1 category and the criteria for selecting the criteria.
- Where a category with a subheading (such as system organ class) has to be split over more than one page, output the subheading followed by "(cont)" at the top of each subsequent page. The overall summary statistics for the subheading should only be output on the first relevant page.

14.2.6. Footnotes

- A solid line spanning the margins will separate the body of the data display from the footnotes.
- All footnotes will be left justified with single-line spacing immediately below the solid line underneath the data display.
- Footnotes should always begin with "Note:" if an informational footnote, or a, b, c, etc. if a reference footnote. Each new footnote should start on a new line where possible.
- Subject specific footnotes should be avoided, where possible.

 Footnotes will be used sparingly and must add value to the table, figure, or data listing.

